In general, unless otherwise specified, events or measurements happen before the randomization date are in Stage 1 and happen on or after the randomization date are in Stage 2. For patients who are not randomized, all events or measurements are in Stage 1. All events happening after visit 14 will not be considered as in Stage 2 for patients who enrolled into bridging visit unless otherwise specified.

D. Definition of Baseline

Baseline Definition

Baseline will be defined as the last non-missing measurement taken prior to the start of stage 1 open-label treatment administration. In the case where the last non-missing measurement and the reference start date coincide and time of measurement is not available, that measurement will be considered Baseline unless the assessment was scheduled to be post-study drug administration in the SOA. Change from baseline is defined as the post-baseline value minus the baseline value, unless specified otherwise. Percent change from baseline = $(\text{Change from Baseline}/\text{Baseline}) \times 100$.

Study Day

Study Day will be calculated from the reference start date within stage and will be used to show start/stop day of assessments and events. Reference start date is defined as the day of first dose (Day 1) in stage1.

Study Day will be computed as follows:

(Confidential)

- Study Day = (date of event - date of first dose in stage 1) + 1 if the date of the event is on or after the date of first dose.
- Study Day = (date of event - date of first dose in stage 1) if the date of the event is prior to the date of first dose.

E. Missing Data

Unless stated otherwise, missing data will not be replaced with imputed values. When relevant, sections below will address how missing data will be handled for the particular analyses.

Analysis Window

All measurements recorded at unscheduled or early termination visits will be mapped according to the windowed visits by actual study day. These records then will be used for analysis if the scheduled ones are missing. If more than one visit occurs within a single visit window, then the analysis will take the one closest to and before the target day. All scheduled assessments will be analyzed according to the protocol defined visits, regardless of the study day

Stage	Study Visit	Study Week	Study Day	Study Day Window
1	Enrollment Visit	1	1	1
1	Virtual Visit 2	2	14	Post-dose - 21
1	Virtual Visit 3	4	28	22 - 35
1	Virtual Visit 4	6	42	36 - 49
1	Visit 5	8	56	50 - 70

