1	Virtual Visit 6	12	84	71 - 98
1/2	In-Person Clinic Visit 7	16/End of Stage 1	112	Patients enrolling in Stage 2: 99 to first dose of Stage 2 Patients not enrolling in Stage 2: 99 - 117
2	Virtual Visit 8	18	126	Post-dose - 133
2	Virtual Visit 9	20	140	134 - 154
2	In-Person Clinic Visit 10	24	168	155 - 182
2	Virtual Visit 11	28	196	183 - 210
2	In-Person Clinic Visit 12	32	224	211 - 238
2	Virtual Visit 13	36	252	239 - 266
2	End of Treatment Visit 14	40	280	266 - 283

Primary Efficacy Endpoint Missing Data Imputation

For patients who do not have BMI value at the end of Stage 1 (Week 16), the unscheduled or early termination weight measurement mapped into Week 16 per visit window will be used for the primary analysis. If weights are measured in triplicate within a same date, the average of the triplicates will be calculated before the BMI calculation. The latest height value will be used together to derive the missing Week 16 BMI.

For patients who still do not have BMI value after above imputation at Week 16, they are treated as non-responder for the primary.

Missing or Partial Adverse Event and Medication Start or Stop Date:

For partial start dates:

- If the year is unknown, no imputation will occur.
- If the year is known and the month and day is unknown, then:
 - If the year matches the year of the first dose date, then impute the month and the day the same as first dose date.
 - If the year is not the same year of the first dose, then month and day will be imputed as 01 January.
- If the month and year is known and the day is unknown, then:
 - If the month and year match the month and year of the first dose date, then impute the day the same as first dose date.
 - If year and month is not the same as the first dose date, then the day will be imputed as "01".

For partial end-dates:

- If the year is missing, no imputation will be performed, and the AE/CM will be assumed as ongoing.
- If the year is present and both month and day are missing and the year is not the same as the last study date, then the month and day will be imputed as the last day of the year, 31 December.
- If the year is present and both month and day are missing and the year is the same as the last study date, then the month and day will be imputed as the last study date.
- If the year and month are present and only the day is missing, and the year and month is not the same as the last study day then the day will be imputed as the last day of the month.

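### SAP V.E imputes partial AE start dates against the Stage 1 first dose only, so unless IX.B says otherwise some Stage 2 AEs default into open-label Stage 1

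*SAP*

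**What the plan says.** SAP V.E has four branches for a partial start date with a known year:

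- Day missing, first-dose month: "If the month and year match the month and year of the first dose date, then impute the day the same as first dose date".
- Day missing, any other month: "If year and month is not the same as the first dose date, then the day will be imputed as" 01.
- Month and day missing, first-dose year: "If the year matches the year of the first dose date, then impute the month and the day the same as first dose date".
- Month and day missing, any other year: "If the year is not the same year of the first dose, then month and day will be imputed as 01 January".

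No branch refers to randomisation or to the first Stage 2 dose. V.E does not say which first dose it means, but V.D does: "Reference start date is defined as the day of first dose (Day 1) in stage1". Where the SAP means the later dose it says so, as in the Week 16 row of the analysis window table: "Patients enrolling in Stage 2: 99 to first dose of Stage 2".

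Stage is then assigned by V.C, under a preface allowing for exceptions: "events or measurements happen before the randomization date are in Stage 1 and happen on or after the randomization date are in Stage 2".

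TEAE tables are split by stage and treatment group. The Concomitant Procedures section refers to a definition of stage for adverse events in IX.B, and the opening of IX.B is redacted. Concomitant Medications (G.2) has its own stage rules, based mainly on end date or ongoing status.

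**The concern.** The trial has two treatment starts, and the imputation rule protects only the first. A partial date in the first-dose month is moved onto treatment. A partial date in the randomisation month is moved to the 1st, which is normally before randomisation.

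The error runs one way. Outside the first-dose branches an imputed start is never later than the true start, and the first-dose branches themselves land in Stage 1. The rule can therefore move a Stage 2 AE into Stage 1 but never the reverse.

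Stage 2 is the only randomised, placebo-controlled part of the trial, and safety at the end of each stage is a stated endpoint. An AE moved in this way leaves the setmelanotide versus placebo summary and is added to the open-label table. SAP V.J also plans an interim analysis of Stage 1 and takes care to keep Stage 2 data out of it. A Stage 2 AE back-dated by imputation would carry a Stage 1 label and could enter that output.

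**Working it through.** The plan gives no figure to reproduce. The check applies V.E and then V.C to every possible date.

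**Inputs**

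- Randomisation on Study Day 112, 111 days after first dose (Protocol 7.2.2).
- Stage 2 from Day 112 to Day 280: 280 − 112 + 1 = 169 days.
- Average month length L = 365/12 = 30.4 days.
- Assumed: first-dose dates equally likely on each day, and Stage 2 onset equally likely on each of the 169 days.

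**Step 1: which branch applies.** No calendar month is as long as 111 days, so randomisation never falls in the first-dose month. The 01 branch always applies to a day-missing date in the randomisation month.

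**Step 2: day missing, within the randomisation month.** A patient randomised on day r of the month has L − r + 1 Stage 2 days in it. All of them are misassigned unless r = 1.

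- Average Stage 2 days in the month: (L + 1)/2 = 15.7.
- Average misassigned days: (L − 1)/2 = 14.7.
- Share misassigned: 14.7/15.7 = 93.6%.
- Patients who escape because r = 1: 1/30.4 = 3.3%.

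**Step 3: day missing, over all of Stage 2.** 14.7/169 = 8.7%. In later months the imputed 1st is still after randomisation, so nothing else moves.

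Enumerating all 881 first-dose dates from 1 October 2021 to 28 February 2024 (an assumed range within the planned trial period) gives the same results: 0 of 881 randomisations in the first-dose month, 29 of 881 on the 1st, 93.6% and 8.7%. Moving randomisation to Day 107 or Day 117, the edges of the visit window, changes neither percentage at this precision.

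**Step 4: year only.** An onset in the calendar year of randomisation goes to the first-dose date or to a 1 January before randomisation. It escapes only if onset falls in a later year or randomisation was on 1 January. With a mean onset of 84 days after randomisation, the share misassigned over whole calendar years is 1 − 84/365 − 1/365 = 76.7%. The 881-date range does not cover whole years and gives 80.7%.

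**Step 5: example.** First dose 1 March 2022, randomised 20 June 2022, AE onset recorded as June 2022 with no day. V.E gives 1 June 2022, and V.C then gives Stage 1.

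**Step 6: medications.** Under G.2 a medication belongs to Stage 2 if its end date is missing, it is ongoing, or it ended on or after Stage 2 dosing. One begun in Stage 2 meets this whatever start date is imputed. With a start imputed to before Stage 2 dosing it also meets the Stage 1 definition, so it is counted in both stages.

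**The case against.** The strongest objection is that the AE result rests on V.C, which yields where something else is specified, and the SAP points to a separate AE stage definition in IX.B. The opening of that section is redacted. Its visible part handles other missing AE data conservatively: missing relationship becomes related, and missing grade becomes Grade 3. It may also settle stage for partial dates. This stands, and the point is conditional on it. What remains is that V.E itself has no Stage 2 step.

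Three stronger readings are tempting, and the documents support none of them.

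- **Medications are lost from Stage 2.** They are not. G.2 keeps them there, and the effect is double counting.
- **The loss is much larger because onset clusters just after the switch.** An exponential onset with mean 28 days would raise the day-missing share from 9% to 38%, but the documents give no onset distribution.
- **The placebo comparison is tilted toward one arm.** The rule does not depend on treatment, and nothing in the documents shows that partial dates differ by arm.

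The Stage 2 schedule also limits the problem. AEs are reviewed on Days 112, 126, 140, 168, 196, 224, 252 and 280, never more than four weeks apart, so an AE with an unknown month should be rare. All AEs are also listed with their period, and V.O allows the analysis plan to be clarified before outcomes are examined by treatment group.

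Finally, simply imputing the first Stage 2 dose date whenever the month matches would reverse the error. On average 14.7/30.4 = 48% of days in the randomisation month are true Stage 1 days, and for year-only dates the exposure is greater. That objection stands and shapes the fix.

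**Conclusion.** The point holds for AEs, conditionally. As far as the visible text goes, V.E has no anchor for the start of Stage 2. Unless IX.B supplies one, an AE that began in Stage 2 with its day missing in the randomisation month is placed in Stage 1, except when randomisation was on the 1st. Under uniform onset this covers 8.7% of Stage 2 onset days. Year-only dates are misplaced in roughly 77% to 81% of cases, depending on the calendar range assumed, but should be few.

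These shares apply only to records with partial start dates. The documents do not say how many there will be, and the number is probably small. Reading the first dose as the Stage 1 dose is a well-supported inference, not V.E's own wording. The consequence is confined to safety and medication tables: the primary endpoint is unaffected and no statistical testing is planned. This is a minor correction worth making before Stage 1 output is produced.

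**What to change.** Add to V.E, or confirm that IX.B already states, a rule for randomised patients whose partial AE start date is compatible with both stages:

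1. Decide stage first from recorded information. An AE with an end date before randomisation, or first reported at or before the Day 112 visit, is Stage 1. One first reported after that visit is Stage 2.
2. Only if the stage is still undetermined, and the known month (or year) matches that of the first Stage 2 dose, impute the first Stage 2 dose date.
3. Apply the same start-date rule to medications, so that a Stage 2 start is not also counted in Stage 1.

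The cost is a few sentences in the SAP and use of the first-report visit in programming. AEs are already reviewed at the Stage 2 Entry Visit, so step 1 should settle most cases. The downside is that a few Stage 1 events reported late may be counted in Stage 2.

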If the year and month are present and only the day is missing, and the year and month is the same as the last study day then the day will be imputed as the last day of the study.

F. Genetic Diversity

It is possible that a patient may enter the trial with more than one eligible gene. In this situation, all eligible genes will be captured in the database. For analysis purposes, a single gene will be considered the "primary gene" for that patient, and the patient will be analyzed within that gene cohort. The primary gene will be defined as the eligible gene with the most

significant American College of Medical Genetics (ACMG) categorization (e.g., Pathogenic>Likely Pathogenic>Variant of Uncertain Significance [VUS]). If two or more eligible genes share the same most significant ACMG categorization, then the “primary gene” will be defined as the least prevalent gene and the patient will be analyzed within that gene cohort.

G. Multiple Study Centers

The study is a multicenter trial. Data from all study sites will be pooled for the purpose of analyses. No adjustment for study center is planned.

H. Covariate Adjustment in Primary Analysis

Covariate adjustment is not applicable for this study as there is not statistical testing for the primary analysis.

I. Data Safety Monitoring Board

The Data Safety Monitoring Board (DSMB) will meet periodically (i.e., every 3 months) to review the cumulative safety data from the study and will make a recommendation to continue or modify the study, if needed. The following unblinded data will be presented to the DSMB members:

- Demographics
- Disposition
- Adverse Events
- 12-Lead ECG
- Injection Site Evaluation
- Skin Examination
- Hyperpigmentation
- Fitzpatrick Classification Scale
- Inclusion/Exclusion Criteria
- Sexual Function (Male)
- Sexual Function (Female)
- Safety Laboratory Data
- Columbia-Suicide Severity Rating Scale
- Patient Health Questionnaire-9

J. Interim Analysis

An interim analysis will be performed when all patients have completed Stage 1 or terminated before Stage 1. All Stage 1 related analyses on this SAP will be summarized.

To avoid any potential bias due to patients still enrolled in the study at the time of the interim analysis, an unblinded team member at ██████████ will be involved in ensuring that any data of the Stage 2 are not included in the interim analysis.

K. Multiple Comparisons

There is no statistical testing planned in this study.

L. Analysis Set

- **Screened Population**

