For continuous outcome measure analyses, a weekly average score will be calculated as an arithmetic mean. The baseline score for Stage 1 will still be arithmetic mean of the available score values within 7 days before or on the first dosing (Day 1). For visits in [Scenario 2], [Scenario 3] and [Scenario 4], arithmetic mean of up to 7 measurements that are closest to and before the scheduled visit date will be calculated. For example, measurements taken between Day 1 (V1) to Day 14 (V2) will be labeled as Day 14 (V2) measurement on the table display.

N. Data Display Characteristics

Data displays produced for this study will include three types—summary tables, data listings, and figures. Unless stated otherwise, data listings will be produced for all recorded data. Summary tables will be produced as specified in following sections. Additional data listings will be produced for outcome measures that involve extensive procedures to derive the analyzed outcomes. Figures will be produced when specified in sections to follow.

Listings in general will be presented by gene cohort, stage, then treatment (active and placebo) unless otherwise specified.

Data listings will simply list the data recorded on the CRF or derived for each patient. When expedient, additional levels of ordering hierarchy may reflect subsets of assessments within patient. Data listings will not display patient initials.

Tables in general will be presented by stage unless otherwise specified. In which stage 1 will be presented by overall, each gene in SEMA 3 gene cohort, and gene cohort, stage 2 will be present by overall, each gene in SEMA 3 gene cohort, gene cohort, and treatment (active and placebo).

Tables may have either of two general layouts. When the greatest interest is in direct comparison of one treatment group with the other at particular times, different columns of a summary table will display the statistics for the different treatment groups. The placebo group statistics will be displayed to the left of the treatment group statistics. When the evolution of statistics over time is of greater concern than comparison at particular moments, a group of rows may be designated for the placebo group; the table columns would be designated for different summary statistics of interest. A subsequent group of rows would then be used for the treatment group. In this layout, a group of rows that represent a treatment group would generally be ordered chronologically.

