- Any medications happening after the dosing date at visit 14 will not be considered as concomitant medication in stage 2

Concomitant medications will be tabulated by ATC Level 2 classification and PT by stage. A patient having more than one medication within the same ATC Level 2 or preferred term will be counted only once for that ATC Level 2 or preferred term.

A listing of prior and concomitant medications will be provided.

H. Concomitant Procedures

Concomitant procedures data will be listed by stage. The definition of stage will follow adverse events in IX.B.

I. Skin Examination

A comprehensive skin examination will be performed by the Investigator at the time points designated in the SOA.

The skin examination should include a full body (head-to-toe skin examination).

Frequency count of most severe outcome across all skin regions within patients will - be provided by stage and visit. The severity of the outcome is rated as Abnormal, CS > Anormal, Not CS > Normal > Not Done.

Also, the frequency count by skin region with abnormal result will be provided.

All skin examination data will be presented in listing.

J. Hyperpigmentation

Hyperpigmentation form will be administered at postbaseline visits.

All hyperpigmentation data will be presented in listing.

K. Sexual Function

Sexual function forms have different versions between male and female. All sexual function data will be presented in listing by version.

L. Electrocardiogram

A single 12-lead electrocardiogram (ECG) is performed at the visits designated in the SOA.

ECG measurements include PR interval (msec), RR interval (msec), QRS interval (msec), QT uncorrected (msec), QT corrected with Bazett's formula (msec), QT corrected with Fridericia formula (msec). Summaries of actual values and changes from baseline of these measurements will be presented.

A frequency and percentage table of normal, abnormal not clinically significant and abnormal clinically significant for overall ECG evaluation will be tabulated.

ECG data will be presented in listing.

M. Columbia-Suicide Severity Rating Scale (C-SSRS)

The C-SSRS that will be administered to patients ≥ 6 years of age according to the SOA.

There are two versions of the C-SSRS forms:

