1. The Baseline/Screening version of the scale is the initial form of the instrument to assess suicidality in a patient's lifetime. This version can assess a patient's lifetime suicidality for data collection purposes as well as eligibility based on inclusion/exclusion criteria.
2. The 'Since Last Visit' version of the scale assesses suicidality since the patient's last visit. This version is meant to assess patients who have completed at least 1 initial C-SSRS assessment and should be used in subsequent visits. The 'Since Last Visit' version of the C-SSRS is inquiries about any suicidal thoughts or behaviors the patient/participant may have had since the last time the C-SSRS was administered.

A frequency and percentage table and a shift from baseline by visit will be provided to display the number of patients who have answered at least one 'Yes' to: Suicidal Ideation (1-5),

Suicidal behavior (6-10), either have suicidal ideation or suicidal behavior (1-10), and the question “Non-Suicidal Self-Injurious Behavior”.

In details, the Suicidal Ideation and Suicidal behavior will include questions as below:

Suicidal Ideation (1-5)

1. Wish to be dead
2. Non-Specific thoughts
3. Ideation without intent to act
4. Ideation with some intent to act
5. Ideation with specific plan

Suicidal behavior (6-10)

6. Preparatory acts or behavior
7. Aborted attempt
8. Interrupted attempt
9. Actual attempt
10. Completed suicide

All C-SSRS data will be listed.

N. Patient Health Questionnaire-9 (PHQ-9)

The PHQ-9 is a 9-item depression scale of the Patient Health Questionnaire and will be used for patients ≥ 12 years of age. After the patient has completed the PHQ-9 questionnaire, it is scored by the trial staff. Any patient with a PHQ-9 score ≥ 10 will be referred to a mental health professional (MHP). The PHQ-9 will be administered according to the SOA.

Summary statistics for the score of summation of the 9 items and changes from baseline will be provided. Frequency count and percentage of number of patients with score ≥ 10 will also be included. Only scores with all 9 items answered will be summarized.

All PHQ-9 data will be listed.

O. Children’s Depression Inventory-2 (CDI-2)

The CDI-2 has both a self-report and a parent version.

The CDI-2: Self-Report Short version is an efficient screening measure that contains 12 items and will be administered to patients < 12 years of age according to the SoA.

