Items on the CDI-2 Parent form correspond to items on the self-report version and are suitably rephrased. Item selection for the parent forms was guided to maximize validity, and thus focused on observable manifestations of depression. The CDI-2 parent form consists of 17 items and the 4 choices provided for each item correspond to 4 levels of symptomatology: 0 (not at all), 1 (some of the time), 2 (often), or 3 (most of the time). The CDI-2 parent version will be administered to caregivers of patients < 12 years of age according to the SoA. Any patient with a CDI-2 score > 20 during the trial will be referred to an MHP.

X. Supplemental Analysis

A supplemental analysis deriving from re-confirmatory genetic diagnosis is conducted for Primary endpoint, and Secondary endpoints of efficacy for patients in Supplemental Analysis Set.

Patients who become ineligible for the trial after the re-confirmatory genetic diagnosis will be excluded from the supplemental analysis.

XI. Pharmacokinetic Analysis

The trough concentration values will be reported descriptively as mean, standard deviation (SD), maximum (Max), minimum (Min), median, and percent coefficient of variation (% CV) based on dose and visit.

The PK concentration and ADA will be listed.

██████████ (Confidential) ██████████ ██████████

XIII. Appendix 1: BMI-for-age charts, 2 to 20 years, LMS parameters and selected smoothed BMI (kilograms/meters squared) percentiles, by sex and age

Sex	Age (months)	L	M	S	P95	Age at Screen
M	24	-2.01118	16.57503	0.080592	19.33801	2
M	36.5	-1.41999	16.0003	0.072634	18.23842	3
M	48.5	-1.71487	15.62817	0.071889	17.83614	4
M	60.5	-2.61517	15.41914	0.075992	17.93893	5
M	72.5	-3.21171	15.38353	0.083048	18.41421	6
M	84.5	-3.32319	15.51287	0.092131	19.15236	7
M	96.5	-3.18306	15.78231	0.102091	20.06793	8
M	108.5	-2.97115	16.16712	0.111721	21.08893	9
M	120.5	-2.76565	16.64614	0.120112	22.15409	10
M	132.5	-2.59056	17.20089	0.126735	23.21358	11
M	144.5	-2.44743	17.81463	0.131389	24.22985	12
M	156.5	-2.32946	18.4718	0.134141	25.17811	13
M	168.5	-2.22736	19.15759	0.135251	26.04662	14
M	180.5	-2.13234	19.85766	0.13511	26.83688	15
M	192.5	-2.03902	20.55765	0.134198	27.56393	16
M	204.5	-1.94913	21.24248	0.133057	28.25676	17
M	216.5	-1.87467	21.89587	0.132286	28.95862	18
M	228.5	-1.83514	22.50072	0.132566	29.72674	19
M	240	-1.84233	23.02029	0.134539	30.58964	20
Sex	Age (months)	L	M	S	P95	Age at Screen
F	24	-0.98661	16.4234	0.085452	19.10624	2

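### The SAP's list of unblinded DSMB data leaves out CDI-2, the only depression scale for ages 6 to under 12, and SAP IX.O specifies no CDI-2 summary

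*SAP*

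**What the plan says.** SAP V.I introduces the DSMB material with "The following unblinded data will be presented to the DSMB members" and names 14 data types. The last two are C-SSRS and PHQ-9. CDI-2 does not appear, and no redaction is marked in the list.

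Protocol 8.9.9 calls for depression to be assessed with PHQ-9 or CDI-2, depending on age. SAP IX.N and Protocol 8.9.9.2 assign PHQ-9 to patients aged 12 or older. SAP IX.O and Protocol 8.9.9.3 assign CDI-2 to those under 12, as a self-report short form plus a parent form.

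SAP IX.N specifies output for PHQ-9: "Summary statistics for the score of summation of the 9 items and changes from baseline will be provided" and "Frequency count and percentage of number of patients with score ≥ 10 will also be included". SAP IX.O describes the two CDI-2 forms and closes with "Any patient with a CDI-2 score > 20 during the trial will be referred to an MHP". Section X follows directly.

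SAP V.N sets the defaults. For listings: "Unless stated otherwise, data listings will be produced for all recorded data". For tables: "Summary tables will be produced as specified in following sections".

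**The concern.** The protocol gives a central nervous system mode of action as its reason for monitoring mood, and it treats the two depression scales as age-matched counterparts. Both carry a cut-off for referral to a mental health professional, and both are scheduled at the same visits in Protocol Tables 1 and 2. The SAP then treats them differently: the older group's scale goes to the DSMB and gets tables, while the younger group's scale does neither. Neither document gives a reason.

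What is at stake is a comparison between arms. In Stage 2 the patient, investigator and sponsor are all blinded (Protocol 7.2.2), so the DSMB is the body placed to set drug beside placebo while the trial runs. A difference in depression scores among children aged 6 to under 12 is not among the things the SAP puts before it. In the final outputs the same scores would appear only patient by patient.

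Stage 1 is not the issue. It is open-label, and investigators and the sponsor review its safety data continuously (Protocol 9).

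**Working it through.** The plan states no figure to reproduce. The check sets the sections side by side.

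**1. Coverage by instrument**

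| Instrument | Ages | Measures | On the V.I list | Output specified |
|---|---|---|---|---|
| C-SSRS (IX.M) | 6 and over | Suicidality | Yes | Frequency and shift tables, listing |
| PHQ-9 (IX.N) | 12 and over | Depression | Yes | Score, change, count at 10 or more, listing |
| CDI-2 (IX.O) | Under 12 | Depression | No | None |

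Enrolment starts at age 6 (Protocol 6.1), so the 6 to under 12 group exists by design and CDI-2 is its only depression scale. Protocol 8.9.9.2 words the PHQ-9 age rule loosely by adding a reference to the schedule, but SAP IX.N limits the scale to 12 and over.

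**2. What the defaults give CDI-2.** Under V.N a table exists only where a section asks for one. IX.O asks for none, so there is no table. The listing default does apply, so the raw scores are reported.

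**3. Does listing-only status explain the omission from V.I?** No. For hyperpigmentation IX.J says "All hyperpigmentation data will be presented in listing", and for sexual function IX.K says "All sexual function data will be presented in listing by version". Neither section specifies a table, yet both items are on the DSMB list.

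**4. How many children this could concern.** The documents do not give the number aged 6 to under 12. Assume a share s of the approximately 100 patients planned for Stage 2 (Protocol 5.1). With 2:1 randomization, the expected numbers are 100 × s × 2/3 on drug and 100 × s × 1/3 on placebo.

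| Assumed share | Children | Drug | Placebo |
|---|---|---|---|
| 5% | 5 | 3.3 | 1.7 |
| 10% | 10 | 6.7 | 3.3 |
| 20% | 20 | 13.3 | 6.7 |

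The shares are assumptions with no source in the documents. The split is an expectation only, since the stratification described is by gene, not age. Dropout and the switch to open-label treatment after a BMI rise of 5% or more (Protocol 5.1.3.2) would lower the numbers at later visits.

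**5. What this implies for the layout.** SAP V.Q defines five gene cohorts. Even at 20%, an even spread gives 6.7 / 5 = 1.3 placebo children per cohort. A table by cohort would carry no information; an overall table would be sparse but readable.

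**The case against.** The strongest objection is that the DSMB works under a separate charter (Protocol 9), which was not available. Both documents describe its task as review of the accumulating safety data, and neither confines it to the 14 items. The list also lacks vital signs, although Protocol Table 3 names changes in vital signs in the safety endpoint. It may therefore be incomplete. This stands, and it limits the point to what the SAP specifies.

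A reader might infer that the DSMB will not see CDI-2, or that mood in the youngest children goes unmonitored. The documents support neither. A child above the cut-off is referred individually. C-SSRS covers everyone from age 6 and is on the list, as are adverse events; under Protocol Appendix 5 a clinically significant abnormality on a safety assessment can be recorded as one. These safeguards are real, but none compares depression scores between arms.

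There are three further objections:

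- With 2 or 3 placebo children, by-visit means would add little to a listing that V.N already orders by cohort, stage and treatment. This is fair for the report at the low end of the range. It does not explain why the DSMB list omits the instrument.
- The blinded data review in SAP V.O could still add a summary. That is true, but it takes place after all data are collected, too late for DSMB meetings.
- The available SAP text loses content elsewhere without a mark: its Stage 1 schedule stops after the hunger questions. A line lost after PHQ-9, the last DSMB item, cannot be excluded. It would take separate losses in V.I and IX.O to remove the point.

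**Conclusion.** The point holds as a minor gap in what the SAP specifies. CDI-2 is absent from the 14-item V.I list and has no summary in IX.O. Followed as written, the SAP provides no arm-level view of depression scores for ages 6 to under 12, either to the DSMB in blinded Stage 2 or in the report. The scores are not lost, because the default listing covers them.

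This rests on the V.I list being used as stated. If the charter already includes CDI-2, the DSMB half falls away and only the missing summary in IX.O remains.

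It would go too far to infer a safety signal or actual harm: the size and direction of any imbalance between arms cannot be derived from the documents. The number of children affected is also unknown. On the assumed shares of 5% to 20% it is 5 to 20, with about 2 to 7 on placebo, so any display would be descriptive only.

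**What to change.** 1. **SAP V.I:** add CDI-2, self-report and parent forms, after PHQ-9. Check that the DSMB charter matches.
2. **SAP IX.O:** for each form, specify summary statistics for the score and for change from baseline, plus the number and percentage above the referral cut-off, by visit and stage, and by arm in Stage 2. The denominator should be children under 12 who completed that form at that visit.
3. **Layout:** state in IX.O that these tables are presented overall only. V.N already provides an overall presentation but adds gene and cohort breakdowns, which would be nearly empty here.

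The cost is SAP wording, one more DSMB output, two table shells and a charter check. The data are already collected, so no assessment or visit is added. The drawback is that the tables will be sparse and must be read as descriptive. The DSMB addition helps only at meetings still to come; the IX.O addition helps the report in any case.
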